8. We will use the oral morphine conversion table to convert any opiate use to OME for each patient (26).
9. Assess possible complications with each intervention (expected to be low).

Study Population

- All female patients undergoing laparoscopic or robotic hysterectomy at MHH and will be recruited and consented for enrollment by the research team in the preoperative area.

Inclusion Criteria:

- English or Spanish speaking
- American Society of Anesthesiologists (ASA) physical status 1-3,
- Age greater than or equal to 18 years
- Planned laparoscopic or robotic hysterectomy

Exclusion Criteria:

- History of chronic pain requiring preoperative opioids, Known alcoholism disorder
- Congenital coagulopathy,
- Localized soft tissue infection,
- Use of anticoagulants,
- Dementia, inability or refusal to provide consent for the surgery
- Morbid obesity (BMI > 50), due to expected technical difficulty to achieve the block.
- Usual pain management will continue regardless of which arm of the study patients are in and measurements of pain scores, narcotic usage and abdominal numbness will be assessed in the post-operative period.

Study Design and Procedures

The study will be reported according to the CONSORT (Consolidated Standards of Reporting Trials) guidelines (28).

All medications and procedures used in this study (0.25% bupivacaine, dexamethasone, acetaminophen, ibuprofen, QL blocks) are FDA approved and have been determined to be usual care in the coverage analysis.

1- Recruitment and consents:

Patients undergoing laparoscopic or robotic hysterectomy at MHH will be recruited and consented for enrollment and block randomized to one of 2 arms: Local anesthesia and QL block. The regional anesthesia nurse would consent the patients.

Spanish consents are available for Spanish speaking patients.

Patients will not be told if they will be receiving the drug or the control.

Blinding is done by the nurse anesthetist preparing the medication, to assure anesthesiologist and research personnel are blinded to the drug used since each patient will receive the two modalities, with only one containing the active drug.

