Three regional anesthesia nurses will be trained to obtain consents. They are the usual medical personnel that currently mix and prepare the medication and they have been doing so for years. They will be drawing the active or the placebo drug in a sterile manner and give the syringes to the "regional" anesthesiologist and the scrub nurse, assuring safety of administration. We have discussed this procedure with [name] the Nurse in charge for the Gyn Surgical Services and she is agreeable with the procedures (Email: [contact])

[figure not shown]
The procedure is done after the patient is placed under general anesthesia assuring blinding for the patient as well as the research assistant who has no access to Care4. Regional anesthesiologist and surgeon are also blinded as they will be handed the medication sterile in a syringe in both cases.

2- Randomization:

It is done in preoperative unit at the time of obtaining consent via redcap set up by the statistician.

The Nurse anesthetist will then prepare the 20 mls syringes and label them (all drugs are visually identical to normal saline) according to the allocation specified by the randomization. See figure 3:

Figure 3:

3- Intervention:

- **The intervention:** is performed by the gynecologist for the local anesthetic, and by the regional anesthesia team for the blocks (only attendings, fellows (under supervision) will be performing the block) under ultrasound guidance.
- As per **current** procedures, the nurse anesthetist will fill the syringes and give them to the regional anesthesiologist for the QL block and the scrub nurse for the local anesthetic.
- For the placebo QL block, the nurse will draw saline and for the study drug she will draw 19 mls of 0.25% bupivacaine and 4 mg of Decadron. Bupivacaine and Decadron are mixed per the same procedure that is currently done, assuring patient safety.
- For the Local anesthetic and to blind the surgeon, the nurse anesthetist will draw the saline 20 mls for the placebo and the 20 mls of 0.25% bupivacaine for the actual local and give it to the scrub nurse via syringe into a sterile cup .

Arm N1- local drug, Sham QL

Arm N2- Sham local, QL drug

	Study drug	Formulation in each syringe
Arm N1	Local	0.25% Bupivacaine X 20 mls
	Sham QL	20 mls of normal saline
Arm N2	Sham Local	normal saline 20 mls
	QL	19 mls of the 0.25% bupivacaine + 1 mls (4 mg of Decadron), totaling 20 mls.

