During the telephone encounters or the clinical visits, patients will be asked if they filled their prescription for Tramadol/narcotic and how many pills they have left). If the patient is not seen at the 2 weeks mark for any reason, a telephone call will be done to collect that information by the surgeon.

6- Expected duration of study and subject participation.

We currently perform at the minimum 5 hysterectomies per week and Memorial Hermann Hospital (Laparoscopic and Robotic) and expect to randomize half of the patients, to complete the study within up to 2 years after IRB approval.

Sample Size and Power

- Based on previous studies, the mean standard deviation of QOR-40 after gynecologic laparoscopy are 150-170 and 10-15, respectively.
- A clinically significant difference would be 10-15.
- A sample size of 31 patients per group is needed to detect the difference of 20 points in the global QOR-40 score, a SD 25, with a Type 1 error of 5% and a power of 90%.
- 76 patients will be included to allow for a dropout rate of approximately 18%. Lost to follow up is expected to be low.

For pain scores in the VAS: Meaningful clinical difference in VAS scores is 30%

Analysis Plan/Statistics

- For baseline patient characteristics, continuous variables will be reported as medians with 25th and 75th percentiles (interquartile range [IQR]), and categorical variables as counts and percentages.
- To compare across groups, Kruskal-Wallis tests will be performed for continuous variables and Chi-square tests for categorical variables.
- CONSORT diagram will be performed
- Intention to treat analysis will be performed
- All unadjusted outcomes will be reported descriptively (mean SD/ median IQR)
- For all outcomes, we will conduct intent-to-treat Bayesian analysis to calculate probabilities of intervention benefits and harms. We will use neutral priors and exclude large treatment effects. We will report posterior medians of group differences, their corresponding 95% credible intervals, and probability of treatment benefit.

Primary outcome as QOR will be analyzed with a negative binomial regression model to account for expected skewness. The model will include group (local, QL), and type of surgery as covariates. We will account for surgery type (Robotic versus laparoscopic hysterectomy) simply because of the difference in port placement and port size between both approaches.

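### The nurses who take consent also prepare the allocated drug under block randomisation, so the recruiters, as a team, know past allocations and can predict later ones better than chance.

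*Combined protocol and SAP*

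**What the plan says.** **Who consents.** Under Study Population, patients are "recruited and consented for enrollment by the research team in the preoperative area". Under 1- Recruitment and consents, "The regional anesthesia nurse would consent the patients", and then "Three regional anesthesia nurses will be trained to obtain consents".

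**Who prepares the drug.** The same paragraph goes on to say of those three nurses: "They will be drawing the active or the placebo drug in a sterile manner and give the syringes to the 'regional' anesthesiologist". Under 2- Randomization, syringes are filled and labelled "according to the allocation specified by the randomization", so whoever prepares them must know the arm. There, in the blinding text and in 3- Intervention, the preparer is called the nurse anesthetist.

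**How allocation works.** Patients are "block randomized to one of 2 arms". On timing: "It is done in preoperative unit at the time of obtaining consent via redcap set up by the statistician". The protocol does not say who operates REDCap. It gives no block size, no varying of sizes and no step that locks enrolment before the allocation is shown.

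**Who is blinded.** The text names the patient, the research assistant, research personnel in general, the regional anesthesiologist and the surgeon. It does not name the nurses who consent and prepare.

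**Flow and analysis.** Section 6 counts at least five hysterectomies a week, of which the investigators "expect to randomize half of the patients". The primary model under Analysis Plan/Statistics contains group and type of surgery.

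**The concern.** Allocation concealment requires that the person deciding whom to approach, and how hard to encourage them, cannot foresee the next arm. REDCap can hide the next entry on the list. It cannot hide the history from people who made up the earlier syringes, and in balanced blocks the history carries information: when one arm is ahead, the other is more likely to come next.

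No bad intent is needed. A nurse who expects a given arm next may encourage one patient slightly more or less than another. The arms could then differ at baseline in anxiety, pain expectation or surgical complexity, none of which the primary model includes. Blinded collection of the 24-hour QoR-40 protects measurement, not the make-up of the groups, and selection at enrolment cannot be repaired afterwards.

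**Working it through.** The plan states no figure for predictability, so there is none to reproduce. The only plan figure used is the total of 76, which agrees with its own inputs: 2 × 31 = 62, and 62 / (1 − 0.18) = 75.6, rounded up to 76.

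**Inputs.** Two arms, permuted blocks, and 1:1 allocation (implied by equal group sizes). Block size is an assumption, taken as 2m with m = 1, 2, 3 and larger values for comparison. The guessing rule is to name the arm that is behind and toss a coin when level. Completed blocks are balanced, so the running difference over all patients equals the difference within the current block. The rule therefore needs the history but not the block size.

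**A. The three nurses pool their history.**

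- Expected correct guesses per block: m + 2^(2m−1) / C(2m, m) − 1/2. Divide by 2m for the rate.
- Expected share of allocations that are certain, if the block size is also known: 1 / (m + 1).

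| Block size | Correct guesses per block | Rate | Certain if size known | Certain, of 76 |
|---|---|---|---|---|
| 2 | 1 + 2/2 − 0.5 = 1.5 | 75% | 1/2 = 50% | 38 |
| 4 | 2 + 8/6 − 0.5 = 2.83 | 70.8% | 1/3 = 33% | about 25 |
| 6 | 3 + 32/20 − 0.5 = 4.1 | 68.3% | 1/4 = 25% | 19 |
| 8 | 4 + 128/70 − 0.5 = 5.33 | 66.6% | 1/5 = 20% | about 15 |
| 10 | 5 + 512/252 − 0.5 = 6.53 | 65.3% | 1/6 = 16.7% | about 13 |

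Check for blocks of 4, by position: 1/2; 2/3; (1/3 × 1) + (2/3 × 1/2) = 2/3; 1. The sum is 2.83, and 2.83 / 4 = 70.8%.

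**B. Pooled history, block sizes mixed at random and unknown.** Simulation of 76 patients with sizes 4/6, 2/4/6 or 4/6/8 gives about 68–70% correct.

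**C. No sharing.** Simulation of 76 patients, each falling at random to one of three nurses who knows only her own cases:

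- block size unknown: about 53% correct;
- block size and boundaries known, sizes 2, 4 and 6: about 58%, 57% and 56% correct, with about 17%, 4% and 1% certain.

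**D. Benchmark.** A recruiter who does not know past allocations is right 50% of the time. Simple randomisation also gives 50%, whatever is known.

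**The case against.** Four objections deserve an answer.

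1. **The nurses may belong to the research team, so the consent sentences need not conflict.** This is a possible reading. But the blinding text says research personnel are blinded, which could not be true of team members who draw the drug. The nurse anesthetist might instead be a separate preparer, yet the consent paragraph expressly says the consenting nurses draw it. The role wording needs reconciling on either reading.

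2. **The high figures assume shared knowledge.** This stands. Any one nurse has prepared only some of the syringes, and without sharing the advantage shrinks to about 53%. Nothing in the protocol prevents sharing among three colleagues at one site, so the upper range is possible but not established.

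3. **Predictability is not bias.** This also stands. The documents contain nothing from which to estimate how far recruiters would act on a guess. The planned baseline table may reveal some imbalance, but it would not correct it.

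4. **REDCap may conceal the current allocation.** Probably so, and nothing suggests that the list can be seen. The risk comes from past allocations.

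A reader might also infer more than the text supports. It does not say that the nurses perform the randomisation; drawing the drug already reveals the arm, so the point does not need this. Nor does it show that half of eligible patients go unenrolled: that forecast is a share of hysterectomies performed, and the remainder may include exclusions and refusals. The room for selective approach is therefore real but unmeasured.

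**Conclusion.** The concern holds as a stated feature of the design: the recruiters are unblinded to earlier allocations, randomisation is in blocks, and no safeguard is described. On assumed block sizes of 2 to 6, correct prediction of the next arm ranges from about 53% (own cases only, block size unknown) to 68–75% (history pooled), against 50% under concealment. Certain prediction of 25–50% of allocations requires both pooled history and a known block size.

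A reader might infer that the nurses can usually tell the next arm, or that the result will be biased by some definite amount. The documents support neither. They support a plausible route to selection bias of unknown size, which adjustment for group and surgery type would not remove. It should be closed before recruitment. Sample size and outcomes are unaffected.

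**What to change.** **Main change.** State that eligibility and consent are completed and locked in REDCap by a member of the research team, for example the study coordinator, who does not prepare study drug and does not know earlier allocations. Only then does the preparing nurse open the allocation and make up the syringes. Delete the sentences that give consent to the regional anesthesia nurses, and use one title for the preparer throughout. This returns the recruiter to 50%.

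**Second step.** Have the statistician use randomly varying block sizes that are not disclosed to site staff. This takes away certain prediction, but on its own it leaves about 68–70% correct guesses if history is shared, so it does not replace the separation of roles.

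**Cost.** Protocol wording and a REDCap setting. The protocol names a research team but does not already require a consenter blinded to earlier allocations, and it does not show that the coordinator or research assistant can cover pre-op on the day of surgery. The sponsor should confirm this; otherwise the change may need extra cover. Scheduling becomes a little less flexible.

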This study aims to compare quality of recovery as well as peri-operative systemic opiates use and pain scores in patients undergoing laparoscopic or robotic hysterectomy when local anesthetic versus Quadratus Lumborum nerve block (QL-2) is added to the standard pain management.

Primary Outcome measure:

For the primary outcome, we plan to Compare the Quality of Recovery (QOR-40) validated questionnaire scores between different arms

a. At 24 hours

The Quality of Recovery-40 (QoR-40) questionnaire measures the quality of recovery from anesthesia through five dimensions: physical comfort, physical independence, emotional state, psychological support, and pain. The validity, reliability, ease of use, responsiveness, and cross-cultural adaptation of QoR-40 have been previously confirmed and this questionnaire has been used successfully in several clinical trials. (27). (Appendix 1). This questionnaire takes 6.3 min to complete and will be filled by the research assistant.

Secondary Outcome measures:

1. *Compare* pain score (rest and dynamic as coughing or moving from lying down to sitting up) between the interventions at several time points: Patients will be instructed to use the visual analog scale (NRS), 0 corresponding to no pain at all and 10 corresponding to worst imaginable pain) at different time points,
 - a. PACU immediately postoperatively
 - b. At the time of first opiate administration,
 - c. At the time of discharge (most patients are discharged the same day)
 - d. On day 1 (24+/-4 hours),
 - e. On day 14
 - f. At 6 weeks
2. To collect these pain scores, the EHR will be used to extract the VAS scores documented by the RN while the patient is in the PACU and until the patient is discharged from the hospital.
3. A telephone call will be done at 24 hours (+/-4 hours) by the research assistant blinded to the procedure and the patient will be seen by the physician in the office at the 2 and 6 weeks mark as per usual care.
4. Compare time to administration of first pain medication in the hospital.
5. Estimate PONV scores (Worst score) before discharge across different interventions. Scale: (none, mild, moderate severe).
6. Compare the time needed to administer the intervention QL Block.
7. Compare opiate use in the postoperative period measured in oral morphine equivalent (OME)
 - a. In the first 24 hours after the surgery (which is the duration of the block).
 - b. 2 weeks post-surgery.
 - c. 6 weeks post-surgery

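### Only the active QL syringe contains Decadron, so the trial compares a drug-and-block package with port-site local anesthetic, and that Decadron is never reconciled with the ERAS line limiting it to non-diabetics

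*Combined protocol and SAP*

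**What the plan says.** All references are to the combined protocol and SAP.

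- **Syringe contents (3- Intervention, text and arm table).** For the QL block, "for the study drug she will draw 19 mls of 0.25% bupivacaine and 4 mg of Decadron"; the placebo QL syringe is saline. For the port sites, "the nurse anesthetist will draw the saline 20 mls for the placebo and the 20 mls of 0.25% bupivacaine for the actual local". The arm table repeats this under the column heading "Formulation in each syringe". The mixture is presented as existing practice: "Bupivacaine and Decadron are mixed per the same procedure that is currently done".
- **Usual care (Study Design and Procedures).** The listed drugs and procedures, dexamethasone and QL blocks among them, "have been determined to be usual care in the coverage analysis".
- **Name of the comparison.** The Objectives compare outcomes "when local anesthetic versus Quadratus Lumborum nerve block (QL-2) is added to the standard pain management". In Analysis Plan/Statistics the model's group term has the levels local and QL, and the reported contrast is local against QL block. None of these mentions Decadron.
- **ERAS.** Block procedures says the standard ERAS protocol applies to all patients. Its intra-operative column lists Decadron 4 mg, restricted to patients without diabetes.
- **Eligibility.** Diabetes is not among the Exclusion Criteria, and diabetes status is a row of the baseline table.
- **Laterality.** Block procedures has the QL block given on both sides.
- **Blinding (1- Recruitment and consents).** The nurse anesthetist prepares the drugs "to assure anesthesiologist and research personnel are blinded to the drug used", and "Regional anesthesiologist and surgeon are also blinded as they will be handed the medication sterile in a syringe in both cases".

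**The concern.** There are two separate issues.

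**What the contrast measures.** The arms differ in the site and technique of injection and also in whether the injectate contains dexamethasone. The Background says that evaluating the efficacy of these blocks could change practice at the institution, so a reader of the results will tend to credit any difference to the block. No section says that a difference belongs to the combination. This applies to the primary outcome (QoR-40 at 24 hours) and to pain, opioid use and PONV among the secondary outcomes.

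**Two Decadron instructions that do not refer to each other.** One is tied to allocation and has no diabetes condition; the other is tied to diabetes status and has no allocation condition. Followed together, they give Arm N2 diabetics a drug that the ERAS line leaves out for diabetics, and give Arm N2 non-diabetics the same drug from two sources. No sentence considers both sources or gives a total. Because the anesthesiologist and the surgeon are blinded, they cannot tell from the allocation whether a patient's QL syringe contains Decadron, so the protocol itself has to say how the two instructions fit together.

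**Working it through.** **Inputs**

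- Active QL syringe: 19 mL of bupivacaine plus 1 mL holding 4 mg Decadron (3- Intervention).
- Active local, sham local and sham QL syringes: 0 mg Decadron (3- Intervention).
- ERAS line: 4 mg in non-diabetics, 0 mg in diabetics, both arms (ERAS table; Block procedures).
- Number of QL syringes per patient, k: not given in the available text. Taken as 1 (one syringe split between sides) or 2 (one per side); this is an assumption.

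**The plan's own figure.** 19 mL + 1 mL = 20 mL, which is the stated total for the active QL syringe. It reproduces.

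**Formula, read literally (block added to ERAS).** Total Decadron = ERAS dose by diabetes status + 4 mg × k if in Arm N2.

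| | Arm N1 | Arm N2, k = 1 | Difference | Arm N2, k = 2 | Difference |
|---|---|---|---|---|---|
| Non-diabetic | 4 + 0 = 4 mg | 4 + 4 = 8 mg | 4 mg | 4 + 8 = 12 mg | 8 mg |
| Diabetic | 0 + 0 = 0 mg | 0 + 4 = 4 mg | 4 mg | 0 + 8 = 8 mg | 8 mg |

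The ERAS dose cancels within each row. The difference between arms is therefore 4k mg whatever share of patients has diabetes, and no prevalence has to be assumed.

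**Can the analysis separate drug from block?** No. Syringe Decadron is 4k mg for everyone given the Arm N2 syringes and 0 mg for everyone given the Arm N1 syringes, so it coincides with allocation. Adding a dexamethasone covariate to the planned model (group and type of surgery) would not recover a block-only effect. The remedy is in the naming of the contrast, not in an adjustment.

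**Does the text fix k?** The arm table is per syringe and the block is bilateral. The blinding sentence speaks of a syringe in the singular, and the section on funding describes the placebo as 20 mL of saline. Both lean towards one syringe, but neither refers to the two sides. The Randomization section sends the reader to Figure 3 for the syringes, and that figure is not available here.

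**The case against.** The strongest reply is that the trial compares two disclosed usual-care packages. The arm table shows the Decadron openly, the text calls the mixture current procedure, and local and QL are shorthand for arms defined in full. This stands: the randomized comparison is valid for the packages, and the protocol nowhere claims an effect of needle technique apart from the injectate. It does not answer the naming point, because the objective and the reported contrast are what will be carried into the conclusions.

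The second reply is that the ERAS relation can be inferred. General Information (PICO) describes the blocks as additions to the ERAS bundle, the Objectives add them to standard pain management, a line under the Exclusion Criteria continues usual pain management in both arms, and ERAS covers everyone. This also stands. A reader might infer that the relation between the doses is wholly unstated, or that the syringe dose might replace the ERAS dose or fall under its diabetes limit. No text supports replacement or an extended limit, and the general statements point to both doses applying as written.

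A reader might also infer that the nurse preparing the syringes has no instruction. The documents do not support that: the instruction is unconditional. What is missing is either a diabetes exception or a statement that none applies. Giving the ERAS dose by diabetes status needs no unblinding.

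Finally, the ERAS table sets a glucose target with hourly checks. That is a safeguard, but it does not say which Decadron instruction governs a diabetic in Arm N2.

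**Conclusion.** The point holds in two parts.

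First, the named contrast omits a drug given through only one arm's study syringes. A difference would support a statement about QL block with bupivacaine plus dexamethasone against port-site bupivacaine, and not about the block alone. The documents give no figure for an effect of dexamethasone on any outcome, so its share of a difference is unknown and is not estimated here. It would go too far to conclude that the comparison is invalid or that a benefit would be due to dexamethasone.

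Second, the syringe Decadron and the ERAS Decadron line with its non-diabetic restriction are never explicitly reconciled. On the literal reading the arms differ by 4 mg with one QL syringe, or by 8 mg with one per side. This rests on both doses applying as written. The 8 mg figure also rests on a syringe count that the available text does not settle and that Figure 3 may. It should not be read as a finding that the plan omits the count.

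The matter should be fixed: it bears on exposure in diabetic patients and on what the trial can conclude.

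**What to change.** 1. The investigators must reconcile the Intervention section, Block procedures and the ERAS table, stating explicitly how the syringe Decadron relates to the ERAS Decadron line and to its non-diabetic restriction. No dose or clinical rule is proposed here.
2. Confirm the number of QL syringes used for the bilateral block, if Figure 3 does not already show it.
3. If the syringe contents stay as written, name the contrast in the objective, the analysis plan and the conclusions as *QL block with bupivacaine plus dexamethasone versus port-site bupivacaine*, and state that differences are not attributable to the block technique alone.
4. Tabulate total dexamethasone by arm and diabetes status as a description of exposure. Because the syringe dose reveals the arm, keep that field from blinded staff until the outcome data are locked.

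The cost is wording in three places, one recorded variable with restricted access, and a narrower claim. Diabetes status is already collected. Sample size, randomization and the primary model are unchanged.

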
NON-Diabetics Carbohydrate load
 
Gatorade 8 oz 2 hours before procedure
 
Clear liquids up to 2 hours prior to surgery
 
Tylenol 1gm PO
 
Celecoxib 200mg PO
 
Gabapentin 300-600mg PO
 
Robaxin 750mg PO
 
Scopolamine unless contraindicated (Avoid in males with prostate issues)
 
Reglan-AVOID with bowel obstructions
	
Standard Induction
 
 Reduction/elimination of narcotics beyond induction. 
Decadron 4mg (in non diabetics)
 
Infusions
 
 Propofol (50-150 mcg/kg/min) +/- Dexmedetomidine (200mg/50ccNS) 0.25-0.5mg/kg IV bolus post-induction, then infusion at 0.1-0.3mg/kg/hr *Consideration: Start at 0.4mcg/kg/hr then decrease after 1 hour to 0.2mcg/kg/hr. During closing, decrease to 0.1 mcg/kg/hr Ketamine 10mg/hr or 0.25mg/kg/hr. If not given per infusion, bolus patient with 50mg prior to incision and 1 hour prior to close. Consider 0.125mg/kg injections q30mins IVP if unable to start an infusion. +/- Inhalation agents (<0.5 MAC if used) Acetazolamide (TBD) Max Fentanyl 150 mcg (consider baseline HR and BP) 	
Last hour of case
 
 Terminate Ketamine infusion Zofran 4mg Closing (fascial) Propofol to 1mcg/kg/hr (bolus as needed) Dexmedetomidine Decrease to 0.1 mcg/kg/hr Pressure Support ventilation 60 % FiO2 	
S
 
Goal directed fluid administration ~3-5cc/kg/hr of isotonic fluids (Avoid Normal Saline)
 
Minimal Use of invasive lines, NGTs, drains, foleys, and tubes
 
Glycemic control Blood sugar less than 200 (Glucose checks q hour)
 
Maintenance of core temperature >36 Optimal 37
 
Prevention/Control of nausea and vomiting
 
Lung protective ventilation. Decreased TVs; Increased PEEP (6-8ml/kg IBW PEEP 6-10)
	
 Acetaminophen 650mg by mouth every 4 hours- Celecoxib 200mg by mouth every 12 hours Gabapentin 300mg by mouth every 8 hour Tramadol 50-100mg by mouth every 6 hours as needed for breakthrough pain (pending phone call) If tramadol is ineffective at controlling breakthrough pain, the pain medication will be escalated to scheduled tramadol 100mg every 6 hours with oxycodone 5-10mg every 4 hours as needed for breakthrough pain dependent upon pain score. Can consider Nucynta 
Ondansetron 4mg IV every 6 hours scheduled
 
Promethazine 12.5mg IM every 6 hours as needed for nausea and/or vomiting etc.

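### The optional dexmedetomidine entry in the ERAS table mixes mg and mcg: its infusion rate as written is 250 to 750 times the start rate beside it

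*Combined protocol and SAP*

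**What the plan says.** Under Block procedures, the protocol says that its standard ERAS protocol applies to all patients, and then sets out the ERAS table. In the first Intra-Op column, dexmedetomidine is listed among the infusions after a plus/minus sign, so it is optional: "Propofol (50-150 mcg/kg/min) +/- Dexmedetomidine (200mg/50ccNS".

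The base regimen is in mg. The bag and bolus read "Dexmedetomidine (200mg/50ccNS) 0.25-0.5mg/kg IV bolus post-induction". The infusion follows, and in the same line the unit changes: "then infusion at 0.1-0.3mg/kg/hr *Consideration: Start at 0.4mcg/kg/hr". The schedule then continues in mcg: "then decrease after 1 hour to 0.2mcg/kg/hr. During closing, decrease to 0.1 mcg/kg/hr". The second Intra-Op column, under the last hour of the case, repeats the closing rate in mcg: "Dexmedetomidine Decrease to 0.1 mcg/kg/hr".

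No other part of the document gives a dexmedetomidine dose.

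**The concern.** The two sets of figures describe the same drug in the same operation, and the hourly rates can be compared directly. One mg is 1000 mcg, so a range of 0.1-0.3 in one unit and a start of 0.4 in the other cannot belong to a single coherent regimen. The reader is given no rule for choosing between them.

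What is at stake is dosing text within the trial procedures. If the source prints what the text shows, anyone who uses the option and follows the base regimen literally would give an hourly dose hundreds of times the one printed beside it. The trial's inference is not at stake.

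**Working it through.** There is no stated ratio in the plan to reproduce. The check is a unit conversion followed by a ratio of hourly rates. No body weight is needed, because every rate is per kg.

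**Inputs, all from the ERAS table**

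| Item | Column | As written |
|---|---|---|
| Bag | first Intra-Op | 200 mg in 50 cc |
| Bolus | first Intra-Op | 0.25-0.5 mg/kg |
| Infusion | first Intra-Op | 0.1-0.3 mg/kg/hr |
| Start (under Consideration) | first Intra-Op | 0.4 mcg/kg/hr |
| Rate after 1 hour | first Intra-Op | 0.2 mcg/kg/hr |
| Rate during closing | first Intra-Op | 0.1 mcg/kg/hr |
| Rate in last hour of case | second Intra-Op | 0.1 mcg/kg/hr |

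**Step 1: convert the infusion.** 0.1 × 1000 = 100 mcg/kg/hr and 0.3 × 1000 = 300 mcg/kg/hr.

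**Step 2: compare with the mcg rates.**

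- Against the 0.4 start: 100/0.4 = 250 and 300/0.4 = 750.
- Against the 0.1 closing rate: 100/0.1 = 1000 and 300/0.1 = 3000.

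The ratio applies to the infusion only. The bag and bolus are not hourly rates. They carry the same factor-of-1000 question: 200/50 = 4 mg/mL as written, or 4 mcg/mL if the unit should be mcg, and a bolus of 250-500 mcg/kg as written, or 0.25-0.5 mcg/kg.

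**Step 3: see what the correction does.** With mg read as mcg, the infusion is 0.1-0.3 mcg/kg/hr. The 0.2 step lies inside that range and the 0.1 closing rate is its lower end. The 1000-fold mismatch is gone.

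**Step 4: ask which set is wrong.** Arithmetic alone does not settle this, since putting every figure in mg would also remove the mismatch. Two features point to the mg entries. The closing rate is given in mcg in two separate columns. And a misread micro sign would turn mcg into mg; it would not produce a spelled-out mcg. The direction should still be confirmed clinically.

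**The case against.** The strongest objection is provenance. The three mg figures are consecutive, and all three fit the rest of the entry once read as mcg. That is the pattern a micro sign misread as m would leave, and a reading error of that kind is not an error in the plan. This stands as a limit on the claim. The partial answer is that mcg is spelled out seven times in the same table: four times for dexmedetomidine, twice for propofol and once for fentanyl ("Max Fentanyl 150 mcg (consider baseline HR and BP"). That evidence is limited, because none of the four dexmedetomidine spellings is in the base regimen; three follow the Consideration note and one is in the other column. The absence of micro signs elsewhere in the table proves nothing, since a misreading would have removed them too.

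The second objection is relevance. The drug is optional, is not a study drug, and is handled alike in both arms. The table reads like a generic handout (it carries a caution for male patients), and it may not be followed line by line: its Post-Op column lists celecoxib, while the prescriptions after the table list ibuprofen. All this stands and keeps the point minor. It does not remove the conflict, because the protocol makes the table part of its procedures.

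A reader might also infer more than the documents support:

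- **That the 0.4 start is a second error**, because it would lie above a corrected 0.1-0.3 mcg/kg/hr range. The table introduces that schedule as a Consideration, which reads naturally as an optional variant.
- **That the propofol closing rate is wrong too**, because "Closing (fascial) Propofol to 1mcg/kg/hr (bolus as needed" uses a different time base from the maintenance rate. No second closing rate contradicts it.
- **That the mg figure would pass unnoticed**, because ketamine, the next drug, is dosed at "Ketamine 10mg/hr or 0.25mg/kg/hr". The dexmedetomidine conflict is visible within its own line.

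**Conclusion.** The point holds as an internal inconsistency in the text as read. The dexmedetomidine infusion is 250 to 750 times the start rate printed next to it, the bag and bolus share the same unit question, and nothing in the protocol resolves it. The ratio is exact and needs no outside figure.

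It rests on one assumption that the available text cannot settle: that the source table prints mg. A reader might infer that the protocol is proven to specify an overdose, or that patients would receive one. The documents do not support either. They do not state a safe dose, they do not call the table an order set, and the unit may be a reading error.

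The severity is minor. There is no effect on the randomised comparison, the sample size or the analysis.

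**What to change.** Check the dexmedetomidine entry in the source ERAS table. If it shows a micro sign, the conflict does not exist in the plan and no correction is needed. If it prints mg, change the bag, bolus and infusion to mcg and have the anesthesia co-investigators confirm the corrected figures.

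The cost is a look at the source and, if needed, a corrected table in a minor amendment. Design, sample size and analysis stay as they are.
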